2.3.2 Pharmacokinetics in Non-Human Primates

After I.V. administration of FP-1305, mean \pm SD C0 (5 minutes post-dosing) was 67.05 ± 6.1 , 731 ± 72.6 and 2755 ± 250.2 μ g/mL following 3, 30 and 100 mg/kg single dosing, respectively. The corresponding AUC_{∞} were 677.2 ± 95.8 , 20683 ± 3241.6 and 144000 ± 20174.2 μ g \cdot h/mL, respectively. The terminal half-life of FP-1305 was 18.3 ± 7.8 , 13.7 ± 7.75 and 23.9 ± 5.9 hours at 3,

30 and 100 mg/kg, respectively. The compound was characterized by low serum clearance and limited volume of distribution.

Before dosing of FP-1305, the percentage of FP-1305 positive CD14+ monocytes in cynomolgus circulation ranged from 50 to 80%. After dosing, the proportion of FP-1305 positive CD14+ monocytes was clearly reduced in all doses indicating that FP-1305 occupies CLEVER-1 in those cells. The number of CD14+ monocytes remained unchanged.

2.3.3 Summary of Pre-Clinical Observations

- CLEVER-1 is present in human and cancer associated lymphatics.
- HEV-like vessels in inflammation and cancer express CLEVER-1.
- CLEVER-1 mediates endothelial transcytosis of immune and tumour cells.
- No clear autoimmune or other phenotype develops in anti-CLEVER-1 treated mice.
- Blocking of CLEVER-1 induces IFN- γ production in antigen specific immune response.
- Cancer progression and metastasis require host CLEVER-1 expression
- Function-blocking antibody against mouse CLEVER-1 has anti-tumour activity
- FP-1305 does not provoke significant adverse events in non-human primates after single-dose I.V. administration at the dose level 100 mg/kg

2.4 Clinical Experience of FP-1305

FP-1305 has not been studied previously in human. This is a first-in-human trial.

2.4.1 Clinical Experience of Macrophage Targeting Agents

Several molecules targeting macrophages (CSF1R or colony stimulating factor 1 antibodies, or small inhibitory molecules against CSF1R) are in development. The frequency of serious adverse events related to these compounds is low. Emactuzumab (RG7155) is a monoclonal antibody that inhibits CSF1R activation. Based on a safety evaluation of 80 patients treated with emactuzumab for solid tumours, one patient experienced a Grade 4 adverse event (a cerebrovascular accident), one patient had Grade 3 Klebsiella sepsis, and one Grade 3 dermatomyositis (Gomez-Roca et al. 2015). AMG 820 is another CSF1R targeting antibody. Twenty-five patients received AMG 820 during a dose escalation study. No serious or fatal treatment-related adverse events were observed (Papadopoulos et al. 2017). Common treatment related adverse events were peripheral/facial/periorbital oedema, asthenia, pruritus, fatigue, decreased appetite, nausea, rash, pyrexia, and diarrhoea (Papadopoulos et al. 2017; Gomez-Roca et al. 2015). Grade 3 asthenia and fatigue were observed in 3 and 1 out of the 80 evaluable patients, respectively, who were treated with emactuzumab (Gomez-Roca et al. 2015). Two patients developed cutaneous and mucosal lesions consistent with subacute lupus erythematosus, but no visceral involvement specific to systemic lupus disease. These patients were treated with hydroxychloroquine and low-dose steroids, which led to rapid clinical improvement. The clinical signs and symptoms resolved without late sequelae in both patients (Cassier et al. 2015).

2.5 Rationale for Tumour Types

The overall rationale for selecting study subjects with certain tumours is based on the non-clinical research. Based on immunohistochemistry analysis, the included tumour types contain macrophages that express CLEVER-1 on their surface. In addition, surrogate antibody targeting mouse CLEVER-1 has demonstrated robust anti-tumour activity for example in a melanoma model.

2.5.1 Hepatobiliary Cancers

Hepatobiliary tumours comprise several major global cancers including hepatocellular (HCC) and biliary tract cancers (Kabbach et al. 2015). Biliary tract cancers are sub-classified into intrahepatic cholangiocarcinoma, originating from the biliary tree within the liver, and extrahepatic cholangiocarcinoma, outside the liver parenchyma; the latter is further subdivided into perihilar cholangiocarcinoma and distal cholangiocarcinoma, with a frequency of 10%–20% intrahepatic, 50% perihilar and 30%–40% extrahepatic cholangiocarcinoma (Valle et al. 2016).

Despite advances in surgical techniques and chemotherapeutic agents, the overall survival in these patients remains extremely poor. Statistics from Cancer Research UK demonstrate that since the 1970s liver cancer rates have more than tripled (236% increase) in Great Britain and a study from two major UK centres demonstrate an overall 5-year survival of less than 20% for these patients (Than et al. 2017).

The Barcelona Clinic Liver Cancer (BCLC) staging system is widely used and encompasses all HCC patients. The system identifies those patients with early HCC who may benefit from curative therapies (stage 0 and A), those at intermediate (stage B) or advanced stage (stage C) who may benefit from palliative treatments and those with a very poor life expectancy (stage D). Median survival without therapy is >36 months for stage 0 and A, 16 months for stage B, 4–8 months for stage C and <4 months for stage D. Over 50% of patients with moderately or poorly differentiated HCC are CLEVER-1 positive and this positivity correlates with low CD8/FoxP3 ratio (see [Figure 2](#) in [Section 2.3](#))

Sorafenib is the standard systemic therapy for patients with advanced HCC and well-preserved liver function (BCLC stage C) and those with intermediate-stage HCC who progress following transarterial chemoembolization. In case of disease progression or intolerance to sorafenib, best supportive care or inclusion into clinical trials for new therapeutic agents are the only options for patients. Systemic chemotherapy, tamoxifen, immunotherapy, anti-androgen or somatostatin analogues are not recommended for the clinical management of HCC patients (Verslype et al. 2012). Thus, there is a high unmet medical need for HCC patients.

Biliary tract cancers comprise <1% of all human cancers and ~10–15% of all primary liver cancers. The preferred treatment is surgery. Systemic chemotherapy, consisting of gemcitabine and cisplatin, is the standard of treatment for advanced biliary tract cancers. There is no established second-line systemic therapy following progression after first-line treatment and patients should be encouraged to participate in clinical trials (Valle et al. 2016).

2.5.2 Pancreatic Cancer

Patients with pancreatic cancer succumb to the disease. Metastases are frequent even when the primary tumour is small, hampering the efficacy of local treatments including surgery and chemoradiotherapy. The available systemic treatments also have limited efficacy. Gemcitabine combined with another agents, such as nab-paclitaxel or S1, or FOLFIRINOX, are often used as the first-line treatment for advanced disease (Cascinu et al. 2010), but the response rates are relatively low and the responses usually short. Moreover, conventional chemotherapy frequently has adverse effects, and not all patients are candidates for chemotherapy due to poor performance status or other reasons. Therefore, there is an unmet need for more effective and well tolerated systemic therapies for patients with pancreatic cancer.

Thus far, results with the current immunotherapies have mostly remained unimpressive in pancreatic cancer. Most pancreatic cancers often do not respond to PD-1 therapy even though cancer mutational rate is often high. This may not be surprising, since pancreatic cancer is characterized with a highly immunosuppressive microenvironment with a high macrophage content. Many patients with pancreatic cancer whose disease progresses on the first-line treatment are candidates for a clinical trial since the efficacy of the currently available second-line systemic treatments remains limited.

The immune microenvironment in pancreatic cancer has also been shown to significantly correlate with tumour stage and prognosis. Advanced and aggressive pancreatic cancers are associated with high levels of regulatory T cells and TAMs (Ikemoto et al. 2006; Ino et al. 2013) many of which are CLEVER-1 positive (Faron data on file). These cancers have been shown to be characterised by a disproportionately high level of Th2 cells (pro-tumour) in comparison to Th1 cells (anti-tumour) cells (Gabitass et al. 2011). Furthermore, preclinical studies have demonstrated a major role for tumour associated macrophages in the progression and metastases of pancreatic ductal adenocarcinomas (Nielsen et al. 2016).

2.5.3 Colorectal Adenocarcinoma

The majority of patients with colorectal cancer have metastatic disease that initially is not suitable for potentially curative resection. The backbone of first-line palliative chemotherapy consists of a fluoropyrimidine (I.V. 5-fluorouracil (5-FU) or the oral capecitabine) in various combinations and schedules. Combination chemotherapy with 5-FU/Leucovorin/oxaliplatin (FOLFOX) or 5-FU/Leucovorin/irinotecan (FOLFIRI) provides higher response rates, longer progression-free survival and better survival than 5-FU/Leucovorin alone. Biological agents against vascular endothelial growth factor and against the epidermal growth factor receptor in combination with chemotherapy further improve the outcome of metastatic colorectal cancer, but also increase the rate of adverse reactions. Epidermal growth factor receptor targeting agents may only be used when patients are tested to have normal (wildtype) RAS genes in expanded gene analysis. The treatment of metastatic colorectal cancer should be approached as a continuum of care in the strategic choice of a regimen or sequence in the different lines. Regorafenib is to be considered a standard option in pre-treated patients. PD-1 blockage in second- or third-line therapy could be considered as a treatment option but only in patients with metastatic deoxyribonucleic acid (DNA) mismatch repair (MMR-deficient) colorectal cancer. The survival of colorectal cancer patients is longer if patients can be exposed to all of the available cytotoxic agents. Therefore, different scenarios of colorectal cancer treatment include even four to five lines of therapy. The choice of the combinations in different lines will depend on the molecular characterisation of the tumour, the goal of treatment, the toxicity of the agents and the knowledge of mutation status of the tumour. Although the outcome of patients with metastatic colorectal cancer has clearly improved during recent years, the median survival is reaching only 30 months in clinical trials. Colorectal adenocarcinoma contains macrophages that are positive for CLEVER-1. In stage IV disease this positivity correlated with poor survival (Algars et al. 2012)

2.5.4 Ovarian Cancer

High grade (type II) ovarian carcinomas are biologically aggressive tumours that do not have a recognised precursor lesion and may arise de novo from the coelomic epithelium. The prototype of type II ovarian cancer is serous carcinoma. Included in this group are high-grade transitional carcinomas, malignant mixed mesodermal tumours, and undifferentiated carcinomas. Type II tumours show considerable genetic instability and TP53 mutations. Hereditary cancers with breast cancer gene (BRCA) 1 or 2 mutations belong to type II tumours (Vang et al. 2009). Practically all macrophages in type II ovarian cancer are CLEVER-1 positive (Faron data on file). There are limited

treatment options for patients with platinum/taxane-refractory disease, as salvage chemotherapy with either platinum-based treatments or other drugs (including topotecan, docetaxel, oral etoposide, liposome encapsulated doxorubicin, gemcitabine, ifosfamide and hexamethylmelamine) produce a modest response rate that is around 10%. Some targeted agents, including bevacizumab and poly (ADP-ribose) polymerase (PARP) inhibitors, such as 41laparib and rucaparib, have been approved for the treatment of advanced ovarian cancer, the PARP inhibitors showing efficacy mainly in patients with BRCA mutation. Yet, cure from advanced (stage IV) epithelial ovarian cancer that is refractory to platinum agents is rare. Patients with such a disease and a good performance status, and who are motivated to receive further treatment, may be considered for experimental trials with new drugs (Colombo et al. 2010). Many ovarian cancers are CLEVER-1 positive (Faron data on file).

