2.5.5 Cutaneous Melanoma

Systemic treatment of advanced cutaneous melanoma has recently substantially improved after the introduction of BRAF inhibitors and immunotherapy with checkpoint inhibitors. Responses to these novel agents are frequent. A subset of patients with advanced cutaneous melanoma treated with checkpoint inhibitors survive for at least 5 years after starting the therapy, which is an important advance in the treatment of this disease that is notoriously resistant to most conventional chemotherapy agents.

There are, however, few effective treatment options for patients with immunotherapy resistant cutaneous melanoma. The response rate for CTLA-4 blockage in treatment naïve patients is around 10%, and the responses with this therapy after the failure of anti-PD-1 treatment are infrequent. Cytotoxic chemotherapy has only very modest efficacy with about 10% response rates in advanced cutaneous melanoma. BRAF-inhibitor therapy alone or in combination with mitogen-activated protein kinase inhibitor is an effective option for patients advanced cutaneous melanoma, if the patient has a cutaneous melanoma with BRAF V600 mutation, but drug resistance will usually emerge. Patients with cutaneous melanoma resistant to PD-1 targeting agents often have high serum lactate dehydrogenase (LDH) levels, which may indicate a low pH in the tumour tissue.

Thus, most patients whose advanced cutaneous melanoma does not respond to immunotherapy, or whose disease progresses on immunotherapy, have few viable treatment options, and may have an immunosuppressive tumour environment with increased CLEVER-1 expression. In addition, mouse anti-CLEVER-1 antibody demonstrates robust anti-tumour activity in B16 melanoma model (Karikoski et al. 2014).

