2.5.7 Gastric adenocarcinoma

Surgical resection of gastric cancer (including GE junction), specifically at early stages, is potentially curative. However, the majority of patients still relapse following perioperative chemotherapy and resection. Patients with inoperable locally advanced and/or metastatic (stage IV) disease should be considered for a systemic treatment (chemotherapy). Doublet combinations of platinum and fluoropyrimidines are generally used and triplet regimens containing anthracycline, platinum and fluoropyrimidine may improve efficacy. Second-line treatment is associated with proven improvements in overall survival and quality of life compared with best supportive care in patients with adequate performance status. In human epidermal growth factor receptor 2-positive gastric cancer trastuzumab in combination with capecitabine or fluorouracil and cisplatin is a standard first line treatment. However, the median overall survival of metastatic gastric adenocarcinoma is approximately 12 months (Smyth et al. 2016).

Immune checkpoint inhibitors demonstrate some activity in unresectable advanced or recurrent gastric or esophago-gastric junction cancer patients refractory to or intolerant to two or more prior chemotherapy regimens. However, the response rates in later line settings are close to 10% and a median overall survival remains poor (approximately 5 months) even though the responders may have long term benefit from the therapy (Kang et al. 2017). Thus, prognosis remains poor in presence of metastatic disease and new treatment approaches are desirable. Based on gene expression analysis, high CLEVER-1 expression correlates with poor survival in gastric adenocarcinoma (Goldman et al. 2018).

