2.6.2 Justification for Design

The proposed trial design enables a flexible approach to identify a safe and tolerable dose which has a biological effect and to expand the cohorts of different tumour types after the dose has been selected. Analysis of the primary efficacy in the expansion cohorts early enough with sufficient statistical power allows for a rapid adaptation of the protocol in order to focus on the tumour types in which the treatment demonstrates the most promising activity. Subject safety will be closely monitored after the first infusion and regularly throughout the trial (see [Section 8.2](#)). The highest dose that can be tolerated (maximum tolerated dose (MTD)) will be first determined using an efficient, adaptive dose-finding design, a modified time-to-event continual reassessment method (TITE-CRM), which allows for more accurate determination of the MTD and shorter trial duration than conventional dose-finding designs (Cheung and Chappell 2000). This initial design allows a simple and rapid escalation scheme (whilst still ensuring safety) in the absence of DLT.

Due to its mechanism of action it is likely that a therapeutic response with FP-1305 will require repeated dosing. Therefore, the trial design is based on repeated infusions in three-week intervals. There is a minimum waiting period of three weeks prior to the recruitment of the next study subject at the same dose level. Both recruited subjects dosed at the first dose level will be observed for a minimum of three weeks for DLT before dose will be escalated into next level.

More subjects may be allocated during Part I to MTD or any dose below it to obtain necessary information for proper dose selection for Part II. It is estimated that a total of 30 subjects will be accrued for the MTD determination during Part I. Detailed PK and PD data will be collected to further inform the optimal dose selection for the expansion cohorts.

Early termination of an individual cohort in case there is no efficacy ensures that subjects are not enrolled into the trial if the treatment is not efficacious. The subject will continue the trial treatment until the participation in the trial is no longer considered to be in the best interest of the subject (as

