15.7 Power Calculations

The operating characteristics of the TITE-CRM will be assessed to assure the design is well calibrated for determining the MTD. Fine-tuning of the model to tailor to the trial's requirements will be aided with the use of the Dose-Transition Pathways, which maps out in advance how the model will recommend doses for all permutations of DLT outcomes for the initial subjects (Yap et al, 2017). Details of the TITE-CRM is presented in the corresponding statistical analysis plan. Part II and Part III are based on adaptive Simon's Two-Stage design, with the following assumptions Type I error rate (α ; one-sided) 0.05, power 0.80, response probability in the palliative treatment 5% (alternative option for these subjects) and response in the trial treatment 20%, 10 subjects in each cohort with at least one subject that demonstrates clinical benefit (CBR by RECIST 1.1 criteria) in the Part II is needed to conclude that the cohort may be expanded. Additionally, data from Part II will be used to determine CLEVER-1 positivity in each of the cohorts. If it is possible that cohorts can be divided in

the CLEVER-1 positive and CLEVER-1 negative groups, both subgroups will be expanded in Part III so that 10 subjects in each group are recruited. In case there are 10/10 non-responders in either of the subgroups, then the recruitment will continue only in the other subgroup with responders. The recruitment can continue within that subgroup until the planned maximum of 29 subjects (or until the required 4 subjects that demonstrate clinical benefit are reached). If the subgroups cannot be defined, the Part III continues with the original cohorts having 1 responder in the cohort. In case there are clearly more negative than positive subjects in some cohort, and also clear difference in the response, the DMC will evaluate the data and decide further cohort expansions.

If the desirable response is obtained in Part III of the trial the cohort(s) may be further expanded.

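### The uniform 5% null in section 15.7 conflicts with the roughly 10% response rate that section 2.5.4 gives for salvage chemotherapy in ovarian cancer, where the rule's one-sided type I error is then at least about 0.29, not 0.05

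*Protocol*

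**What the plan says.** Section 15.7 bases Parts II and III on Simon's two-stage design with one-sided alpha 0.05 and power 0.80. One null serves all tumour types: "response probability in the palliative treatment 5% (alternative option for these subjects"). The alternative is "response in the trial treatment 20" per cent. No source and no tumour-specific value is given. A cohort may expand if there are "10 subjects in each cohort with at least one subject that demonstrates clinical benefit (CBR by RECIST 1.1 criteria) in the Part II". Sections 15.6 and 15.7 then set a maximum of 29 subjects, with 4 required. SAP Part II section 7 repeats the 1/10 trigger and the 29-subject total without giving a null rate.

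The background sections give response rates for existing treatments:

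- **Ovarian cancer (2.5.4):** salvage chemotherapy options in platinum/taxane-refractory disease "produce a modest response rate that is around 10" per cent.
- **Cutaneous melanoma (2.5.5):** "Cytotoxic chemotherapy has only very modest efficacy with about 10% response rates in advanced cutaneous melanoma".
- **Gastric cancer (2.5.7):** for immune checkpoint inhibitors, "the response rates in later line settings are close to 10" per cent.

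Section 2.6.2 says that early termination of a cohort "ensures that subjects are not enrolled into the trial if the treatment is not efficacious".

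**The concern.** Section 15.7 defines its null as the response rate of the palliative alternative. For ovarian cancer, section 2.5.4 describes such an alternative, salvage chemotherapy after platinum and taxane have failed, and puts its response rate at about twice the null. The two sections address the same quantity and disagree.

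If 10% is nearer the truth, a drug no better than salvage chemotherapy passes the rule far more often than 1 time in 20. The first-stage stop is also weaker than the design implies. That stop is the protection on which section 2.6.2 relies, and section 15.7 allows cohorts with a desirable Part III response to be expanded further.

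**Working it through.** **Inputs.** First stage: 10 subjects, continue if at least 1 success (15.7). Final: 29 subjects, at least 4 successes (15.6, 15.7). Null 5%, alternative 20% (15.7). Ovarian background rate about 10% (2.5.4). Because the text says only that the rate is around 10%, 8% and 12% are shown as an assumed range.

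**Formulas.** For a true success probability p:

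- Stop after ten = (1 − p)^10.
- Pass = P(X1 ≥ 4) + sum over x = 1, 2, 3 of P(X1 = x) × P(X2 ≥ 4 − x), with X1 ~ Bin(10, p) and X2 ~ Bin(19, p).

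Ending accrual once 4 successes are reached does not alter the pass probability, because it is the same event as having at least 4 among 29.

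**The plan's own figure, p = 0.05.**

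- x = 1: 0.3151 × 0.0665 = 0.0210
- x = 2: 0.0746 × 0.2453 = 0.0183
- x = 3: 0.0105 × 0.6226 = 0.0065
- x ≥ 4: 0.0010
- Pass = 0.0468. Stop after ten = 0.95^10 = 0.599.

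At p = 0.20 the pass probability is 0.8011. A search over two-stage designs for 5% against 20%, with alpha at most 0.05 and power at least 0.80, returns this same 10/29 rule as Simon's optimal design. The arithmetic of section 15.7 is therefore right for its inputs.

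**At the ovarian background rate, p = 0.10.**

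- x = 1: 0.3874 × 0.2946 = 0.1141
- x = 2: 0.1937 × 0.5797 = 0.1123
- x = 3: 0.0574 × 0.8649 = 0.0496
- x ≥ 4: 0.0128
- Pass = 0.2889 (terms rounded). Stop after ten = 0.90^10 = 0.349.

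**Range.**

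| True rate | Pass (type I error) | Stop after ten |
|---|---|---|
| 5% | 0.047 | 0.60 |
| 8% | 0.17 | 0.43 |
| 10% | 0.29 | 0.35 |
| 12% | 0.41 | 0.28 |

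**Which endpoint.** The background rates are response rates, while the rule counts CR, PR or SD. Every objective responder also has clinical benefit, so the clinical benefit rate cannot be below the response rate. Pass rises with p and stopping falls with p. At a 10% response rate, 0.29 is therefore a lower bound on the rule's error and 0.35 an upper bound on its stopping probability. The documents give no null rate for clinical benefit, so the bounds cannot be tightened from them.

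**What 4/29 excludes.** The exact 90% interval (the level in section 15.3.3) for 4/29 has a lower limit equal to the 5th percentile of Beta(4, 26), which is 4.9%. This does not exclude 10%. The 95% level named in section 15.4 would give a still lower limit.

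**The case against.** The best defence of 5% is eligibility. Inclusion criterion 5 requires that no curative, effective or suitable option exists. Section 2.6.1 describes patients who have used up licensed treatments, and section 15.1 describes a population with no standard option left. For them, a null below the response rate of treatments already tried could be reasonable. That argument is open to the sponsor, but the protocol does not make it: section 15.7 ties the 5% to the palliative alternative, and section 2.5.4 puts a number on that alternative for ovarian cancer.

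A reader might infer that three cohorts are contradicted. The documents do not support that:

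- **Melanoma:** the 10% is for chemotherapy in advanced disease generally, whereas the cohort is limited to immunotherapy-resistant disease. Section 2.5.5 calls CTLA-4 responses after anti-PD-1 failure infrequent and gives no rate for them.
- **Gastric:** the 10% belongs to later-line checkpoint inhibitors, which section 2.5.7 credits with some activity. They are not shown to be the palliative treatment meant in section 15.7.

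These figures suggest that 5% may also be too low there, but no more. A combined false-positive chance across the three cohorts would need 10% to be the right null in each, and is not established.

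It is also fair to say that one null for a set of exploratory cohorts is a design judgement, and that advancement is partly discretionary (section 4). Both points lower the stakes. Neither makes the stated alpha correct for ovarian cancer. Finally, the wording in section 2.6.2 is too strong even at 5%, where about 40% of null cohorts continue, so it is not itself evidence for a 10% null.

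**Conclusion.** The point holds for the ovarian cohort. On the protocol's own background figure, the one-sided type I error is about 0.29, roughly six times the stated 0.05, and the probability of stopping after ten is 0.35, not 0.60. At 8% the error is still 0.17, more than three times nominal.

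This rests on taking section 2.5.4's rate as the null that section 15.7 describes, on independent subjects with a common success probability, and on one cohort run to 29 without the Part III split by CLEVER-1 status. The figures refer to objective response and are bounds for the clinical benefit rule as written. For cutaneous melanoma and gastric cancer they serve only as a sensitivity range.

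A reader might also infer that the plan treats 4/29 as proof of superiority to existing treatment, and that a higher bar such as 7/29 is needed. The documents make no such claim: a desirable Part III response means that the cohort may be expanded further. A 7/29 bar would also clash with ending accrual at 4, and would have power of only 0.35 at a true 20%. It is not recommended.

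**What to change.** In protocol section 15.7 and SAP Part II section 7:

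1. State the null rate per tumour type, with its basis.
2. For ovarian cancer, either use about 10% in line with section 2.5.4, or justify 5% explicitly from the eligibility criteria.
3. For ovarian cancer at 10%, report for the present rule a type I error of at least 0.29 and a probability of stopping after ten of at most 0.35.
4. Show the same figures for cutaneous melanoma and gastric cancer as a sensitivity range, labelled as resting on indirect evidence.
5. State which endpoint the figures refer to: they are computed for objective response and are bounds for CR, PR or SD.
6. Say that 4/29 in the ovarian cohort is a signal for further expansion that does not exclude a 10% rate (exact 90% lower limit 4.9%).

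In section 2.6.2, replace the assurance that early termination prevents enrolment on an ineffective treatment with the stopping probabilities: 0.60 at 5% and 0.35 at 10%.

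Keep the enrolment rule and both thresholds. This is a change of wording with no extra patients. The cost is that the stated error rate for the ovarian cohort becomes less favourable.
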